# 10.5. Appendix 5: RECIST (version 1.1) Tumor Assessment Criteria

At baseline, individual tumor lesions will be categorized by the investigator as either measurable or not, according to the criteria summarized below:

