5.2.5. Measurable Disease

A patient will be considered to have measurable disease if there is at least one target lesion identified at baseline meeting the following criteria:

- Non lymph node lesions with longest diameter ≥ 10 mm by CT scan,
- Non lymph node lesions with longest diameter ≥ 10 mm caliper measurement by clinical exam,
- CNS lesions with longest diameter ≥5 mm provided by gadolinium contrast enhanced MRI perfomed with contingent slices of 1 mm, or
- Lymph nodes with short axis ≥ 15 mm when assessed by CT.

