5.2.8. Adequate Baseline Tumor Assessment

Adequate baseline is defined using the following criteria:

- All baseline assessments must be within 28 days prior to and including the date of first dose.
- All documented lesions must have non-missing assessments (ie, non missing measurements for target lesions and non missing lesions status at baseline for non-target lesions).
- Measurable disease at baseline (see Section 5.2.5 for the definition of measurable disease)

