5.2.9. Adequate Post Baseline Tumor Assessment

An adequate assessment is defined as an assessment where a response of CR, PR, SD, non-CR/non-PD, or PD has been provided by ICR or can be programmatically derived based on investigator's assessment of tumor data for the analyses by ICR or investigator, respectively. Timepoints where the response is not evaluable or no assessment was performed will not be used for determining the censoring date.

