6. ANALYSES AND SUMMARIES

6.1. Primary Endpoint

6.1.1. Confirmed OR by ICR

Analysis set: ITT: All enrolled participants who take at least 1 dose of Lorlatinib

Analysis methodology:

• Objective Response Rate (ORR) defined as the percentage of patients with a confirmed best overall response (BOR) of CR or PR according to RECIST v1.1

BOR will be determined based on reported overall responses at different evaluation timepoints by the independent radiologist from the date of treatment start until documented disease progression or start of new anti-cancer therapy, according to the following rules:

- CR = at least two determinations of CR at least 4 weeks apart and documented before progression and start of new anti-cancer therapy
- PR = at least two determinations of PR or better (and not qualifying for a CR) at least 4 weeks apart and before progression and start of new anti-cancer
- SD (for patients with at least one measurable lesion at baseline) = at least one SD assessment (or better and not qualifying for CR or PR) ≥ 6 weeks after date of treatment start and before progression and the start of new anti-cancer therapy
- Non-CR/Non-PD (for patients with only non-target disease at baseline) = at least one Non-CR/Non-PD assessment (or better and not qualifying for CR or PR) ≥ 6 weeks after date of treatment start and before progression and the start of new anti-cancer therapy
- PD = progression ≤ 14 weeks after date of treatment start and not qualifying for CR, PR or SD
- Not Evaluable (NE) = all other cases.

Clinical deterioration will not be considered as documented disease progression.

- patients without documented CR or PR will be considered as non-responders
- Exact CI for a binomial proportion for ORR using the Clopper-Pearson method
- best % changes vs baseline as defined below under Summaries used for Reporting DMB02-GSOP-RF02 4.0 Statistical Analysis Plan Template 01-Nov-2018 PFIZER CONFIDENTIAL Page 24 TMF Doc ID: 98.03

• % change vs baseline across visits as defined below under Summaries used for Reporting

Intercurrent events and missing data:

- data on response after subsequent anti-cancer therapy is administered will be excluded
- participants with death prior to first post-baseline assessment, inadequate baseline assessment, new anti-cancer therapy started prior to first post-baseline assessment, and all post-baseline disease assessments missing will also be considered as non-responders.

Summaries used for reporting:

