6.2.7. PFS by ICR/INV

Analysis set: ITT: All enrolled participants who take at least 1 dose of Lorlatinib

Analysis methodology:

PFS is defined as the time from date of first dose to the date of the first documentation of PD per RECIST v1.1 as assessed by ICR/INV or death due to any cause, whichever occurs first and will be summarized in months:

PFS (months) = [date of event or censoring-date of treatment start +1]/30.4375.

PFS data will be censored as follows:

- For participants who start a new anti-cancer therapy prior to an event, censoring will be at the last adequate tumor assessment (see Section 5.2.9) prior to the start of new anti-cancer therapy. Note: if date of progression occurs on the same date as the start of new anti-cancer therapy, the progression will be counted as an event.
- For participants with documented progression or death after two or more missing tumor assessments, censoring will occur at the last adequate tumor assessment prior to the missing assessments. In this study antitumor activity will be assessed through radiological tumor assessments conducted at screening and every 6 weeks until disease progression regardless of initiation of subsequent anti-cancer therapy. The allowable time window for disease assessments is ±1week while on treatment and whenever disease progression is suspected (eg, symptomatic deterioration). Therefore time without adequate assessment is defined as 98 days (12 weeks plus 2 weeks).
- For participants who do not have an adequate baseline tumor assessment or who do not have any post-baseline tumor assessments, censoring will occur on the date of first dose unless death occurred on or before the time of the second planned tumor assessment (ie, on or before day 98) in which case the death will be considered an event. Note for participants who died without any post baseline assessments and meet the definition of two or more missing assessment the reason for censoring will be documented as two or more missed assessments and censoring will occur on the date of first dose.
- All other participants alive without objective progression will be censored on the date of the last adequate tumor assessment.

DMB02-GSOP-RF02 4.0 Statistical Analysis Plan Template 01-Nov-2018 PFIZER CONFIDENTIAL Page 28 TMF Doc ID: 98.03 The date of tumor response at each nominal timepoint based on the ICR/INV assessments will be used for determining the dates of last adequate assessment for censoring purposes.

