The censoring and event date options to be considered for the PFS analysis are presented in Table 2.

Table 2.	Outcome and	event dates	for PFS	analyses
----------	-------------	-------------	---------	----------

Scenario	Date of event/censoring	Outcome
No adequate baseline assessment	date of first dose	Censored ^a
Progression or death \leq 98 days after last adequate tumor assessment or \leq 98 days after date of first dose	Date of progression or death	Event
Progression or death > 98 days after the last adequate tumor assessment ^b	Date of last adequate assessment ^b documenting no	Censored
No progression	PD prior to anti-cancer therapy or missed assessments	
New anti-cancer therapy given prior to PD	therapy of missed assessments	

^a if the participant dies \leq 98 days after date of first dose the death is an event on the death date

^b if there are no adequate post-baseline assessments prior to PD or death, then the time without adequate assessment should be measured from the date of first dose; if the criteria were met the censoring will be on the start date.

Summaries used for reporting:

Kaplan-Meier estimates (product-limit estimates) will be presented together with a summary of associated statistics including the median PFS time with two-sided 95% CIs. The PFS rate at 12 months will be estimated with corresponding two-sided 95% CIs. The CIs for the median will be calculated according to Brookmeyer and Crowley and the CIs for the survival function estimates at the timepoints defined above will be derived using the log(-log) method according to Kalbfleisch and Prentice (conftype=loglog default option in SAS Proc LIFETEST). The estimate of the standard error will be computed using Greenwood's formula.

Frequency (number and percentage) of participants with each event type (PD or death) and censoring reasons will be presented along with the overall event and censor rates. Reasons for censoring will be summarized according to the categories in Table 3. If a participant meets multiple definitions for censoring the list will be used to define the hierarchy.

Hierarchy	Condition	Censoring Reason
1	No adequate baseline assessment	No adequate baseline assessment
2	Start of new anti-cancer therapy before event.	Start of new anti-cancer therapy
3	Event more than 98 days from last adequate post-baseline tumor assessment/start date	Event after missing assessments ^a

 Table 3.
 Censoring Reasons and Hierarchy for PFS analyses

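### SAP 5.2.8 makes measurable disease part of an adequate baseline, so a participant with only non-target disease by ICR is censored at first dose for ICR PFS and TTP even if progression is documented

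*SAP*

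**What the plan says.** SAP 5.2.8 requires baseline imaging within 28 days before or on the day of first dose, no missing data on documented lesions, and "Measurable disease at baseline (see Section 5.2.5 for the definition of measurable disease". Under SAP 5.2.5 a participant is "considered to have measurable disease if there is at least one target lesion identified at baseline" that meets the size criteria. A CNS lesion of at least 5 mm on qualifying MRI is enough.

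For PFS without an adequate baseline, SAP 6.2.7 states that "censoring will occur on the date of first dose unless death occurred on or before the time of the second planned tumor assessment". Table 2 repeats this in its first row, with a footnote that for a death within 98 days "the death is an event on the death date". Table 3 puts "No adequate baseline assessment" at the top of the censoring hierarchy. For TTP, SAP 6.2.8 and Tables 4 and 5 follow the same pattern.

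Other parts of the SAP treat participants without target lesions as assessable:

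- SAP 5.2.9 defines an adequate post-baseline assessment as "an assessment where a response of CR, PR, SD, non-CR/non-PD, or PD has been provided by ICR" or derived from investigator data.
- SAP 6.1.1 defines the best-response category "Non-CR/Non-PD (for patients with only non-target disease at baseline) = at least one Non-CR/Non-PD assessment" and reports it for non-measurable disease at baseline.
- SAP 6.5.1 tabulates measurable disease, yes or no, by both ICR and INV.

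Inclusion criterion 4 requires a measurable extracranial target lesion. Protocol Appendix 5 leaves that classification to the site: "At baseline, individual tumor lesions will be categorized by the investigator as either measurable or not".

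**The concern.** An adequate baseline should mean that later scans can be compared with it. For progression, that needs a complete and timely lesion inventory, and a measurable lesion is not essential. Under the present definition, a participant with full imaging and progression documented by ICR can be recorded as censored on the day of first dose.

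The rule also treats outcomes unevenly. In PFS, an affected participant who dies by day 98 is kept as an event, while one who progresses at any time, or stays progression-free, is dropped. Who remains in the analysis then depends on outcome.

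The ICR and INV results could also differ because of the rule rather than the disease. Entry already requires a measurable lesion as judged at the site, so the criterion should rarely matter in the INV analyses.

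**Working it through.** No stated figure in the plan lies behind this point; the only planned number used is N = 70. The check has two parts.

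**1. Tracing one participant through the rules.** Take a participant with a measurable lesion by the investigator, only non-target disease by ICR, complete scans, and a new lesion reported by ICR at week 24 (an invented example).

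- SAP 5.2.5: no qualifying target lesion by ICR, so no measurable disease.
- SAP 5.2.8: third condition fails, so the baseline is not adequate.
- SAP 5.2.9: each earlier non-CR/non-PD reading is nevertheless an adequate assessment.
- Protocol Appendix 5, non-target and new-lesion definitions: the new lesion is progression. These definitions are the relevant support; Appendix 5 Table 5 is introduced for cases with both target and non-target lesions.
- SAP 6.2.7, Table 2 row 1, Table 3 rank 1: PFS censored at first dose.
- SAP 6.2.8, Table 4 row 1, Table 5 rank 1: TTP censored at first dose.

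SAP 2.1.2 defines the PFS and TTP estimands in all treated participants and lists two intercurrent events after which data are excluded: new anti-cancer therapy and an extended assessment gap. Absence of a target lesion is not among them. Protocol 9.4.1 also censors an inadequate baseline at the start date for PFS and TTP, but does not tie adequacy to measurability. That link appears only in the SAP.

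**2. Size, under assumptions.** Let k be the number with no target lesion by ICR. The documents do not give it; I take k = 2 to 7 of 70 (2.9% to 10%). The early-death exception is ignored here.

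*Precision.* A participant censored at first dose adds nothing to the Kaplan-Meier estimate, so the standard error grows by about √(70/(70 − k)):

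- k = 2: √(70/68) = 1.015, about 1.5% larger.
- k = 7: √(70/63) = 1.054, about 5.4% larger.

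In one simulated data set (70 exponential times, mean 240 days, cut off at 500 days), censoring 7 at day 1 gave a median of 184 days. That is the same as analysing the other 63 alone; all 70 gave 181 days.

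*Shift in 12-month PFS.* With S₁ the rate in those with measurable disease and S₂ the rate in those without, and no other censoring before 12 months, the current rule estimates S₁ where all 70 would give ((70 − k)S₁ + kS₂)/70. The difference is k(S₁ − S₂)/70. With assumed S₁ = 35%:

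| S₂ (assumed) | k = 2 | k = 7 |
|---|---|---|
| 60% | −0.7 points | −2.5 points |
| 35% | 0 | 0 |
| 20% | +0.4 points | +1.5 points |

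The sign depends on the prognosis of those removed.

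**The case against.** The strongest reply is that the case may hardly arise. Every participant must have a measurable extracranial lesion, eligibility waivers are not permitted, and the documents do not describe how ICR selects lesions. SAP 5.2.8 names no reader. The Non-CR/Non-PD wording may also partly serve the intracranial analysis: SAP 6.2.2 applies the same response rules to all participants with brain lesions, and leptomeningeal disease is eligible but non-measurable.

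Much of this stands. The trigger is inferred and its rate could be near zero. But SAP 6.1.1 reports Non-CR/Non-PD in the overall response table, and SAP 6.5.1 tabulates measurability separately by ICR and INV, so the plan allows for the case. Reading 5.2.8 by reader is the natural interpretation, given 5.2.9 and 6.5.1.

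A reader might go further and infer that the primary endpoint is compromised, because a confirmed CR in non-target disease meets the best-response rule while the inadequate baseline makes the participant a non-responder. The documents do not support that. SAP 3.1.1 and 6.1.1 say that an inadequate baseline is scored as non-response, which is pre-specified and conservative. Nor does it help to note that 30/70 responders gives an exact 95% lower limit of 31.1% and 29/70 gives 29.8%. That contrast holds for any single reclassified participant and does not measure this rule's effect.

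**Conclusion.** The conflict within the SAP is real for ICR PFS and TTP. The baseline rule discards progressions and follow-up that SAP 5.2.9, SAP 6.1.1 and Protocol Appendix 5 treat as valid. The conclusion assumes that 5.2.8 is applied to each reader's own data and that ICR finds no target lesion, CNS lesions included, in at least one participant.

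The likely effect is small. With 2 to 7 of 70 affected, standard errors rise by roughly 1% to 5%. Under the survival rates assumed above, 12-month PFS moves by between −2.5 and +1.5 points. It would be wrong to conclude that the current rule makes ICR PFS look longer, since the direction is not established. It would also be wrong to say that affected participants never contribute, since a death by day 98 counts in PFS. PFS and TTP are descriptive secondary endpoints, and the study's decision rule concerns ORR alone.

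**What to change.** In SAP 5.2.8, state that for PFS and TTP an adequate baseline means imaging within the 28-day window and non-missing assessments of all documented lesions, by the reader whose data are analysed. Progression by non-target or new lesions is then an event, and non-CR/non-PD assessments count as follow-up under 5.2.9 as it stands. Keep the present three conditions for the ORR non-responder rule, and say so, so that the primary analysis does not change.

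When editing 6.2.8, also reconcile a separate conflict. Its text makes an early death without an adequate baseline a TTP event, while Table 4 and the TTP definition do not.

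The cost is a short SAP revision and a small programming change, with no new data. The downside is that ICR PFS and TTP may look slightly better or worse than under the current rule.

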5.2.9. Adequate Post Baseline Tumor Assessment

An adequate assessment is defined as an assessment where a response of CR, PR, SD, non-CR/non-PD, or PD has been provided by ICR or can be programmatically derived based on investigator's assessment of tumor data for the analyses by ICR or investigator, respectively. Timepoints where the response is not evaluable or no assessment was performed will not be used for determining the censoring date.

5.2.10. Unscheduled Assessments

Unless otherwise specified, unscheduled assessments will not be displayed in summary tables by nominal visit/timepoint. Unscheduled assessments will be used when deriving baseline and worst case on-treatment for Adverse Events. Additionally, unscheduled tumor assessments will be used for efficacy analyses (eg, defining date of progression/censoring, best overall response).

5.2.11. Standard Derivations and Reporting Conventions

The following conversion factors will be used to convert days into weeks, months or years: 1 week = 7 days, 1 month = 30.4375 days, 1 year = 365.25 days.

Percentages will be reported to one decimal place. The rounding will be performed to closest integer / first decimal using the common mid-point between the two consecutive values. Eg,5.1 to 5.4 will be rounded to an integer of 5, and 5.5 to 5.9 will be rounded to an integer of 6.

5.2.12. Analyses for Binary Endpoints

Binary endpoints will be summarized by percentage rates along with two-sided 95% CI using the Clopper-Pearson method (exact CI for a binomial proportion). Waterfall plots will be used to visualize best %change vs baseline in sum of baseline target lesion diameters, Spider plots to visualize %change from baseline in sum of baseline target lesion diameters across visits.

5.2.13. Analyses for Continuous Endpoints

Continuous variables will be summarized using descriptive statistics i.e., number of nonmissing values and number of missing values [i.e., n (missing)], mean, median, standard deviation (std), minimum, maximum, first and third quartile (Q1 and Q3), InterQuartile Range.

In case the analysis refers only to certain visits, percentages will be based on the number of participants with an assessment at that visit, unless otherwise specified.

5.2.14. Analyses for Categorical Endpoints

Qualitative variables will be summarized by frequency counts and percentages. Unless otherwise specified, the calculation of proportions will include the missing category. Therefore counts of missing observations will be included in the denominator and presented as a separate category.

In case the analysis refers only to certain visits, percentages will be based on the number of participants with an assessment at that visit, unless otherwise specified.

5.2.15. Analyses for Time-to-Event Endpoints

Time to event endpoints will be summarized using the Kaplan-Meier method and estimated survival curves will be displayed graphically when appropriate. Graphs will describe the number of participants at risk over time. The median, quartiles, and probabilities of an event at particular points in time will be estimated by the Kaplan-Meier method. Confidence intervals for medians and quartiles are based on the Brookmeyer-Crowley method. Confidence intervals for the estimated probability of event at a particular timepoint will be generated using the log(-log) method with back transformation to a confidence interval on the untransformed scale. Summaries of the number and percentages of participants with an event will also be provided on summary tables and figures.

5.3. Methods to Manage Missing Data

Unless otherwise specified, all data will be evaluated as observed, and no imputation method for missing values will be used.

Any imputations will occur at the analysis dataset level. Additionally, in all patient data listings imputed values will be presented and flagged as imputed.

Missing statistics, e.g. when they cannot be calculated, should be presented as 'ND' for not done, 'NR' for not reached or 'NA' for not applicable. For example, if N=1, the measure of variability cannot be computed and should be presented as 'ND' or 'NA'.

5.3.1. Missing Dates

For purposes of data listings, dates will reflect only the information provided by the investigator on the CRF.

DMB02-GSOP-RF02 4.0 Statistical Analysis Plan Template 01-Nov-2018 PFIZER CONFIDENTIAL Page 20 TMF Doc ID: 98.03 If start dates for adverse events or concomitant medications are completely missing, a worstcase approach will be taken whereby the events will be considered treatment emergent and the medications will be considered concomitant. If only partial information is available (e.g. only a month and year or only a year), and the partial information provides sufficient information to indicate the dates are prior to the start of study treatment (e.g. month/year less than month/year of first dose), then these will be considered to have started prior to treatment; otherwise a similar worst case approach will apply and these will be considered to have started after treatment.

Date of Last Dose of Study Treatment

No imputation will be done for first dose date. Date of last dose of study treatment, if unknown or partially unknown, will be imputed as follows:

- If the last date of study treatment is completely missing and there is no End of Treatment (EOT) CRF page and no death date, the participant should be considered to be ongoing and use the data cutoff date for the analysis as the last dosing date; or
- If the last date of study treatment is completely or partially missing and there is EITHER an EOT CRF page OR a death date available (on or prior to the data cutoff date), then impute this date as the last dose date:

= 31DECYYYY, if only Year is available and Year < Year of min (EOT date, death date),

= Last day of the month, if both Year and Month are available and Year = Year of min (EOT date, death date) and Month < the month of min (EOT date, death date), or

= min (EOT date, death date), for all other cases.

Missing or Partial Death Dates

Missing or partial death dates will be imputed based on the last contact date:

- If the entire date is missing it will be imputed as the day after the date of last contact (see derivation of date of last contact in section 5.2.4); or
- If the day or month is missing, death will be imputed to the maximum of the full (nonimputed) day after the date of last contact and the following:
 - Missing day: 1st day of the month and year of death, or
 - Missing day and month: January 1st of the year of death.

Date of Start of New Anti-cancer Therapy

Anti-cancer therapies will be collected in short term follow up only (up to 35 days after treatment discontinuation)

Incomplete dates for new anti-cancer therapy will be imputed as follows and will be used to determine censoring dates for efficacy analyses:

- The end date of new anti-cancer therapy will be included in the imputation for start date of new anti-cancer therapy. If the end data of new anti-cancer therapy is:
 - completely missing then it will be ignored in the imputations below,
 - partially missing with only year available then the imputations below will consider 31DECYYYY as the end date of the new anti-cancer therapy, or
 - partially missing with only month and year available then the imputations below will consider the last day of the month for MMMYYYY as the end date of the new anti-cancer therapy.
- For participants who have not discontinued study treatment at the time of the data cutoff date, last dose of study treatment is set to the data cutoff date in the imputations below.
- If the start date of new anti-cancer therapy is completely or partially missing then the imputed start date of new anti-cancer therapy is:

= 31DECYYYY, if only Year is available and Year < Year of min [max (PD date + 1, last dose of study treatment + 1), end date of new anti-cancer therapy]

= Last day of the month, if both Year and Month are available and

Year = Year of min [max (PD date + 1, last dose of study treatment + 1), end date of new anti-cancer therapy]

Month < Month of min [max (PD date + 1 day, last dose of study treatment + 1 day), end date of new anti-cancer therapy]

= min [max (PD date + 1, last dose of study treatment + 1), end date of new anticancer therapy], for all other cases.

AE Onset Date

The following imputation rules apply if the event is unique for a participant or it is the first of a series of similar events; otherwise, the AE Onset Date will not be imputed:

- If the AE Collection Date is not missing, is less than the Date of First Exposure to Treatment, and is less than the AE Stop Date, then AE Onset Date is set to the Date of AE Collection.
- If the Previous Visit Date is greater than the Date of First Exposure to Treatment and less than the AE Stop Date, the AE Start Date is set to the previous visit date. DMB02-GSOP-RF02 4.0 Statistical Analysis Plan Template 01-Nov-2018 PFIZER CONFIDENTIAL Page 22 TMF Doc ID: 98.03

- If the Date of First Exposure to Treatment is greater than the previous visit date and less than the AE Stop Date, the AE Onset Date is set to the Date of First Exposure to Treatment.
- Otherwise AE Onset date is set to the AE Stop date.

AE Stop Date

Ongoing events will have the AE Stop Date set to one of the following values:

- Date of Death, if the participant died and a date of death exists.
- Maximum of (Participant Withdrawal date, AE Onset Date, AE Collection Date) if the participant withdrew from the study and a date of withdrawal exists.
- Maximum of (AE Onset Date, Subject Summary Collection Date, AE Collection Date) if the Subject Summary CRF page exists but a date of withdraw does not exists.
- Maximum of (Last Treatment Date, AE Onset Date) if no Subject Summary page exits.

Imputation will only occur if event is unique for the participant, or it is the last of a series of similar events; otherwise the Stop Date will not be imputed. Adverse Events are deemed similar if they have the same verbatim term.

Resolved events will have the AE Stop Date set to the maximum of the AE collection date and the AE Onset date.

Other Missing or Partial Dates

Imputation methods for other partial dates are as follows:

- If the day of the month is missing for a start date used in a calculation, the first day of the month will be used to replace the missing date.
- If both the day and month are missing, the first day of the year is used.
- For stop dates, the last day of the month, or last day of the year is used if the day or day and month are missing, respectively.
- If the date is completely missing, no imputation will be performed.

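### SAP 5.3.1 discards a known month when a partial last-dose or new-therapy date falls in an earlier year than its reference date, so the imputed date lies outside the reported month

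*SAP*

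**What the plan says.** SAP 5.3.1 (Missing Dates) imputes two kinds of partial date against a reference date.

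- **Last dose.** If there is an End of Treatment (EOT) page or a death date, the reference is the earlier of the two dates. A year-only report is handled by "31DECYYYY, if only Year is available and Year < Year of min (EOT date, death date". A report with month and year is handled by "Last day of the month, if both Year and Month are available and Year = Year of min (EOT date, death date", with the further condition that the reported month is before the reference month. Everything else takes "min (EOT date, death date), for all other cases".
- **Start of new anti-cancer therapy.** The branches have the same shape. A known month is kept only under the condition "Year = Year of min [max (PD date + 1, last dose of study treatment + 1), end date of new anti-cancer therapy", again with an earlier month. The fallback is "min [max (PD date + 1, last dose of study treatment + 1), end date of new anticancer therapy], for all other cases". If the therapy end date is "completely missing then it will be ignored in the imputations below", the reference is simply the later of PD + 1 and last dose + 1. Imputed start dates "will be used to determine censoring dates for efficacy analyses".

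These dates are used later in the SAP. Section 6.5.3.1 computes treatment duration as last dose minus first dose plus 1, and duration is the denominator of dose intensity (DI) and hence of relative dose intensity (RDI). Section 6.2.7 censors PFS at the last adequate assessment before a new therapy that starts ahead of the event; progression on the start date itself counts as an event. Section 6.2.8 repeats this for TTP, and 6.2.5 applies the PFS rules to DoR.

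**The concern.** The three branches do not cover every partial date. If month and year are known and the year is before the reference year, the year-only branch does not apply because the month is available, and the month branch does not apply because the years differ. The date drops to the fallback, which ignores the reported month. More information then gives a worse date than less.

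The SAP does better elsewhere in 5.3.1: for adverse events and concomitant medications it compares month and year together with the month and year of first dose. Its closing rule for other partial dates keeps a known month, but it covers only dates without a rule of their own and so does not repair these two.

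At stake are treatment duration and, through the new-therapy date, whether a participant is an event or censored for PFS, TTP and DoR. The last-dose date also enters the new-therapy reference, so an error in the first rule can carry into the second. The documents make the situation possible: follow-up runs for 12 calendar months after the last participant's first visit (protocol 4.4), so the study crosses at least one New Year, and protocol 7.1.1 foresees up to 42 days between last dose and discontinuation for unresolved toxicity.

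**Working it through.** The plan gives no figure to reproduce, so the check applies the written branches to dates. All dates below are illustrative; the documents give none.

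**Last dose.** Reported DEC 2021, day missing; EOT 12 Jan 2022; no death. Reference = 12 Jan 2022.

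- Year-only branch: fails, the month is available.
- Month branch: fails, 2021 is not 2022.
- Fallback: 12 Jan 2022.
- Had the site reported only 2021: 2021 < 2022, so 31 Dec 2021.
- Overstatement of duration: 12 Jan − 31 Dec = 12 days at least, and 12 Jan − 1 Dec = 42 days at most.

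**Effect on RDI, under an assumption.** First dose 1 Jul 2020, last dose reported NOV 2020, EOT 8 Jan 2021. The written rule gives 8 Jan 2021 and a duration of 192 days; the end of the reported month gives 30 Nov 2020 and 153 days, a difference of 39 days. If cumulative dose is fixed at 100 mg × 153 = 15,300 mg whatever date is imputed, DI = 15,300 / 192 = 79.7 mg/day and RDI = 79.7% against 100%. If cumulative dose is itself built up to the imputed date, numerator and denominator grow together and RDI hardly moves.

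**New therapy, therapy end date missing.**

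| Case | Reported start | Last dose | PD | Reference date | Imputed start | PFS |
|---|---|---|---|---|---|---|
| Across New Year | DEC 2021 | 20 Dec 2021 | 10 Jan 2022 | 11 Jan 2022 | 11 Jan 2022 | event |
| Within one year | MAY | 20 May | 10 Jun | 11 Jun | 31 May | censored |
| Across New Year, year only | 2021 | 20 Dec 2021 | 10 Jan 2022 | 11 Jan 2022 | 31 Dec 2021 | censored |

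In the first row the reference is max(10 Jan + 1, 20 Dec + 1) = 11 Jan 2022. Every day of December 2021 precedes the PD date, so the plan's own censoring rule calls for censoring; the imputed start falls one day after PD and makes it an event.

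**Same first row, therapy end date 5 Jan 2022.** Reference = min(11 Jan, 5 Jan) = 5 Jan 2022. The imputed start is outside December but still before PD, so the case stays censored. The switch therefore needs an end date that is missing or not before PD.

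**Reported month later than the reference.** PD and last dose 10 Jan 2022, therapy FEB 2022, no end date: the month is not earlier, so the fallback gives 11 Jan 2022. This too is outside the reported month, but PD still precedes the start and event status does not change.

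**Exhaustive check.** Both rules were coded literally. Each month of 2020 was crossed with every reference date in 2020 and 2021 not earlier than that month, 6,764 combinations. All 12 × 365 = 4,380 cross-year combinations gave a date outside the reported month; none of the 6,764 − 4,380 = 2,384 same-year combinations did. These counts show that the fault is systematic across the year boundary. They do not estimate how often it will occur.

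**The case against.** The best case on the other side accepts the branch logic and disputes its importance.

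- **Few cases.** The fault needs a missing day, a known month and a year boundary. New therapies are collected only up to 35 days after discontinuation (SAP 5.3.1), and other systemic anti-tumor therapy is not permitted on treatment (protocol 6.5.1). A switch also needs therapy begun before PD and no early end date. This stands, and it limits the size of the point. It does not make the case unforeseen: protocol 1.3.3 continues scans after a stop without progression, and SAP 6.2.7 has scans continuing regardless of subsequent therapy.
- **Data checks.** Monitors verify source data (protocol 10.1.7), tablets are counted (protocol 6.4), and imputed values are flagged in listings (SAP 5.3). These reduce the number of partial dates, but they do not change what the rule does with one.
- **RDI.** A reader might infer that RDI is always understated. The documents do not say whether cumulative dose depends on the imputed last-dose date, so only the effect on duration follows directly.
- **Adverse-event window.** A reader might infer that a start imputed too early closes the on-treatment period, costing at least 21 days (11 to 31 January) in the February example. SAP 5.3.1 names only efficacy censoring as the use of the imputed date, so this is not established.
- **Primary endpoint.** SAP 6.1.1 excludes responses after new therapy, so a reader might infer a threat to ORR. That would require an assessment that counts towards confirmation to fall between the true and the imputed start, before PD. No such case is shown.

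**Conclusion.** Wrong as written. In both rules, a month-and-year date in a year before the reference year is imputed outside the reported month. This follows from the text and needs no assumption about the data.

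The size is limited. In the December example, treatment duration is overstated by at least 12 days. DI and RDI are lowered only if cumulative dose is recorded independently of the imputed date. When the therapy end date is missing or not before PD, a PFS, TTP or DoR case that should be censored can become an event, depending on whether the dates straddle New Year.

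The number of participants affected is not given and is probably small. For scale, one participant is 1/70 = 1.4% of the planned PFS and TTP set. At the design target of 43% there would be about 0.43 × 70 = 30 responders, so one is about 3% of the DoR set. Nothing in the documents shows a change in the primary ORR decision.

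**What to change.** In both rules of SAP 5.3.1, compare year and month jointly with the year and month of the reference date:

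- Reported year-month earlier than the reference: last day of the reported month.
- Reported year-month equal: the reference date.
- Year only, in an earlier year: 31 December of that year, as now.
- New therapy only, reported year-month later than a reference set by PD + 1 or last dose + 1: first day of the reported month, but never later than a known therapy end date. If the reported start month is after the end date, query the site. The cap matters because the current minimum prevents a start after the end, and an uncapped first-of-month rule would lose that protection.

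With this change, the last-dose example becomes 31 Dec 2021, and the December new-therapy example becomes 31 Dec 2021 and is censored, matching its within-year twin. A year-only therapy start in a year after the reference year would still take the reference date and is best queried.

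The cost is an edit to two rules in the SAP and in the derivation program, with no new data and no change to the primary endpoint definition. Protocol 9.4 has the SAP finalized before database lock, so the edit should be made by then.
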